### **Posttest assessment**

All measures listed in the Pre-test assessment protocol will be included at posttest except those measures listed under “Intake and review of forms” and “Screening measures”

### **3-month follow-up assessment**

All measures listed in the Pre-test assessment protocol will be included at 3-month follow-up except those measures listed under “Intake and review of forms” and “Screening measures”

During all testing sessions:

1. **Rest breaks** – Participants will be frequently prompted and given rest breaks regularly and as needed.
2. **Adherence to medication schedules** – As medication management can significantly impact the safety of the individual as well as the outcomes of the data collection sessions, individuals will be instructed to maintain their medication schedules during testing procedures.
3. **Safety protocol during testing** - To minimize risks to participants during evaluation sessions, a spotter to assist in preventing falls will be present as needed and a gait belt can be donned as necessary. Testing staff will also be prepared to provide first aid for minor injuries and to contact emergency healthcare personnel in the event of a more serious injury. In the event of a more serious, life-threatening emergency, the emergency protocol described below will be implemented.

### **Participant Renumeration**

At the conclusion of the study, participants will be offered the option of keeping the bike and tablet or returning the bike and tablet and receiving \$400. All participants will be allowed to keep the VívoSmart 3 they were given at the beginning of the study. If the individual was also asked to participate in the normal care control wait-list group they will be eligible for an additional \$50.

The prorated payment schedule for those not in a wait-list group:

Baseline assessment only - \$50

Baseline assessment plus 2 months –\$100

Baseline assessment plus 4 month – \$200

Baseline assessment plus 6 month – \$300

Baseline, 6 months and posttest – Fitbit + \$300

Baseline, 6 months exercise, posttest and 3-mo follow-up - \$400 + VívoSmart 3 or  
Bike, tablet and VívoSmart 3

The prorated payment schedule for wait-list group:

Initial assessment only - \$50

Initial and baseline assessment - \$100

Initial and baseline assessment plus 2 months - \$150

Initial and baseline assessment plus 4 month - \$250

Initial and baseline assessment plus 6 month - \$350

Initial and baseline assessment, 6 months and posttest - VívoSmart 3 + \$350

Initial and baseline assessment, 6 months exercise, posttest and 3-mo follow-up - \$450 + VívoSmart 3 or  
Bike, tablet and VívoSmart 3  
+ \$50.

### **Safety Monitoring Plan:**

A detailed Data and Safety Monitoring Plan has been established following the guidelines of the UW-Madison ICTR Data Monitoring Committee. The DSMP is included as Appendix IV.

#### Steps to Minimize Risks during data collection

To minimize the risks to participants during the data collection sessions, the following risks have been identified and precautions will be taken.

- a. Physical Risks: Fatigue is the most common or frequent physical risk as some of the participants may currently be relatively sedative. Additionally, there is a possibility of a fall and injury during the assessment.
  - a. Steps to Physical Risks: Fatigue: frequent breaks are scheduled in the protocol. Additionally, participants will be informed that they may request a break at any time.

Falls: All participants will be closely monitored by trained study personnel during data collection sessions. Those individuals who are older or who have indicated a recent fall will be asked to wear a gait belt.

#### Steps to Minimize Risks during Exercise, and the Safety/Emergency Protocols

To minimize the risks to participants during the exercise intervention, a number of measures and precautions will be taken. All participants will be asked during the phone screen if they have ever been told that they should not exercise or if they have any reason to believe that they should not exercise. Each individual will complete a medical and health history form covering musculoskeletal, cardiovascular, respiratory, and other health

conditions and provide a thorough list of prescription medications. If any contraindications for exercise are reported, the individual will be instructed to review the exercise protocol with their physician prior to study enrollment and provide documentation asserting that the individual is cleared for exercise. Financial assistance for a necessary screening visit to a medical provider is available. Prior to beginning all legs of the study that involve the cycling intervention, all individuals will have their maximum and target heart rate calculated and will be provided with their individual results. This table will be posted on the bike so that it is visible at all times.

During scheduled exercise sessions, a study team member will monitor the participant's heart rate and perceived exertion (Borg Rating of Perceived Exertion (RPE) (Borg, 1970); appendix II) for the duration of the session. Outside of these scheduled sessions and in the solo cycling group, participants can make use of the reference card to monitor their heart rate and RPE, both of which have target ranges which are highlighted in the information sheet (appendix V and VI). All participants will be asked to complete a daily exercise log (Appendix III). Logbooks entries will be collected from all participants at four week intervals and reviewed by the study team. Any indication of significant discomfort, exercise intolerance, a desire to stop or a medical emergency will result in termination of the session. All research staff will be familiarized with the main signs and symptoms of adverse events and will know to follow the emergency and non-emergency protocols described below.

- B. Physical Risk: Common physical risks include muscle soreness, fatigue and shortness of breath. Less common physical risks include falls, heat intolerance, and skin irritation from the activity monitor. Rare but possible risks include cardio-vascular related events (sudden cardiac arrest, myocardial infarction, and stroke).
  - a. Steps to decrease physical risks –To minimize the risks of muscle soreness, we will follow appropriate guidelines for exercise by including a warm-up prior to the start of each training period, and ending with a cool-down period. We will also recommend participants keep a towel nearby and we will encourage hydration, before, during, and after exercise.

To minimize excessive fatigue and shortness of breath, the intensity of the cycling session will be gradually increased and based upon the participant's previous results and anecdotal reports of fatigue before, during, and after exercise. Additionally, we will use the Borg Rating of Perceived Exertion (RPE) (Borg, 1970) and the maximum and target heart rate formulas described above to monitor participants' exercise response as well as to help individuals monitor their target and

maximum heartrate values on their own throughout the sessions. Participants may terminate a session at any time.

To minimize skin irritation due to the wearing of the Garmin VivoSmart activity tracker, participants will be instructed to wear the monitor snugly, but not too tight on their preferred wrist. Participants will be told to remove the device and place it in a pocket if it cannot be donned comfortably.

To minimize the risk of falls, we will utilize a customized recumbent bike, specifically fit to the individual rider, with a wider seat for more stability, handlebars on the seat, and a lower ground profile that allows participants easy entry and exit without necessitating a step over a central support. Two members of the research team will set-up the bike and properly fit it to the individual rider. Additionally, the team will ensure the stationary bike is set-up in a safe and secure manner and in an area free of clutter and dangerous obstacles.

For heat intolerance, we will encourage participants to exercise in either an air-conditioned room, or in front of a fan. And as previously mentioned, the Borg Scale and HRR will be used to monitor exertion, and target heart rate intensities. Participants may terminate a session at any time.

Given that the proposed intervention is an aerobic protocol, there is the risk for cardio-vascular related events (sudden cardiac arrest, myocardial infarction, and stroke). To minimize these risks, all participants will be asked if they have ever been told that they should not exercise or if they have any reason to believe that they should not exercise during the phone screen. Further, all participants will complete a medical and health history form covering musculoskeletal, cardiovascular, respiratory, and other health conditions and provide a thorough list of prescription medications. If any contraindications for exercise are reported, the individual will be instructed to review the exercise protocol with their physician prior to study enrollment and provide documentation asserting that the individual is cleared for exercise. Financial assistance for a necessary screening visit to a medical provider is available.

TAge-defined heart rate targets will be calculated and each individual in all groups will be informed of their target heart rate zones. To continuously monitor HR, each participant will don a Garmin VivoSmart 3 which provides beats per minute heartrate data and each bike includes a handlebar sensor for participants to grasp and receive a read-out of current HR. An informational sheet has been provided to instruct the participants about the use of heart rate zone calculations and perceived exertion levels (appendix V and VI). All individuals regardless of assigned group will be instructed to target a moderate exercise level. Moderate heart rate values are individual specific. Moderate RPE values are between 3 and 5. During monitored sessions, the research assistant will continuously monitor heart rate and will enquire about RPE at 5 minute intervals. These values will be compared to his/her target HR and RPE. **All participants will be informed that any sessions can/will be terminated by the researcher or participant at any time. The emergency protocol (detailed below) will be implemented if necessary.**

- C. **Psychosocial Risks:** Loss of confidentiality – One potential risk of participating in this study is that confidential information about the participants may be accidentally disclosed. If a participant's current diagnosis of PD is not known to others, the potential to cause damage to their psychological well-being as well as to their reputation exists.

Frustration: Participants may become frustrated with the assessments as the complete battery may take up to 3 hours to complete.

Embarrassment: Individuals may be embarrassed if they are unable to perform a task or if they stumble or fall during the performance of a task.

**Suicidality:** The identification of suicidal thoughts is possible due to the depression questionnaire. In the case of identified suicide risk, the study team will immediately call 911. This will compromise the confidentiality of the participant and the participant will be notified of this breach of confidentiality.

- a. **Steps to Psychosocial Risks: Confidentiality:** All possible care will be taken to maintain confidentiality. No subject will be identified in any report or publication. All data will be coded at the time of data collection. All participants will be assigned an identification number prior to data collection and all documents and files will be named using this ID. All data will be stored on computers which will be kept in the SMIL. All data analysis will be performed on computers in the SMIL or in the faculty office of the PI. A password is necessary for access to the computers and they all are equipped with automatic log off. Data being moved from one location to another will be moved via UW Box or the College of Education's secure network. Only members performing research have access to these computers, therefore identification of any subjects or data is unlikely. Coded data will be kept indefinitely.

Data will be stored/banked for future research projects in a double secured location. In a locked filing cabinet or a password protected computer within a locked room. Coded data will be stored on the School of Education servers indefinitely. It will be used for future research related to exercise studies in the lab. Data may be shared with researchers outside the UW. [name] will be responsible for deciding when/to whom to disseminate coded data, and will work with other researchers if necessary to confirm that they have proper IRB approval/etc., as necessary. Required UW-Madison IRB approval would be obtained prior to the release of any data.

**Contact information:** Each participant will have a sealed folder which contains their emergency contact information including instructions for the local 911 operator and contact information for an identified contact person. During the scheduled sessions, the research team member will be given access to the participant folder for the duration of the session. The sealed folders marked with the participant names will be kept locked in the PI's research office. These folders are to be unsealed only in the case of an emergency. All folders and their contents will be destroyed once the individual completes the three-month follow-up or if they withdraw from the study.

Personal privacy during testing sessions will be maintained by testing in a private room and limiting the people within the research lab to current employees or students associated with the lab.

**Frustration:** To minimize the risk of frustration with the data collection sessions frequent breaks will be provided as will snacks and water during the testing sessions. Additionally, the testing sequence provides a variety of tasks to complete. If it appears that an individual is becoming frustrated with the given task, that task can be stopped or paused and a different task can be completed without disruption of the data collection session.

**Embarrassment:** The PI and her team all have experience working with individuals at an increased risk of falls. The study team will also talk with the individual to minimize the extent to which they feel embarrassed. We will minimize the likelihood of falling by using proper spotting techniques.

**Depression:** The risk associated with learning that you are depressed or suicidal based on the Beck Depression Inventory score is difficult to minimize. The study team will follow the developed protocol

## Protocol in the Event of an Emergency During Data Collection Sessions in the UW – Natatorium

In the case of a medical emergency, a study team member will call 911, while a second team member stays with the participant. Standard lab operating procedure requires two individuals to be present in the lab during data collection sessions.

### Protocol in the Event of an Emergency During Monitored Cycling Sessions – Call 911

- a. Emergency preparedness – All research staff involved in the proposed intervention will be familiarized with the signs and symptoms of a medical emergency. As part of each participant's information folder, we will also have an emergency preparedness plan, which will include the following information:
  - The 10-digit telephone number to contact emergency services (the equivalent of 911) in the participant's local area
  - Special instructions to be given to emergency providers to access the individual in their home setting (i.e. gate codes or entrance locations).
  - Contact information for the participant's caregiver or emergency contact person
- b. Emergency response – The researcher will call 911 immediately if a participant presents with signs of a medical emergency or is unable to verbally respond. We will also call 911 if the participant falls and hits his/her head with or without loss of consciousness, or is unable to get up or move limbs. Once 911 has been contacted, the researcher will continue to monitor the situation via the bike's digital interface, while simultaneously contacting the participant's emergency contact. When emergency responders arrive, the researcher will provide any known details of the event, along with any requested information as noted in the preparedness plan. This information can be conveyed via the Skype connection or to the 911 operator during the call.

### Follow-up Protocol

- a. Termination of session – In the event a participant ends the session early, or reports “not feeling right,” “not feeling well”, “feeling tired,” or any comment that might cause concern, or the participant greatly exceeds their maximum heart rate for an extended period, the researcher will discontinue the session. If the participant's heart rate is within an acceptable exercise recovery range and they are not in distress, a follow-up call will be made to the individual 1 hour later. The participant's emergency contact will be called to advise him/her of the situation if the individual has not recovered by the 1 hour phone call.
- b. Initiation of follow up phone calls (1 hr, 4-6 hrs, and 24 hrs) – The researcher will follow up with the participant and/or his/her emergency contact one hour after an exercise session in which the individual reports not feeling well and once again the following day (24-hour period). The emergency procedure noted above will be initiated if necessary.

**Outside of monitored sessions, individuals are instructed to call 911, if they feel a medical emergency is occurring. For non-emergency medical situations, it is recommended that individuals consult their regular physician.**

## Power and Statistical Analysis

As this is a pilot study, we have not proposed a recruitment level that will properly power the outcome measures for a desired effect size. Previous work by [name] during her post-doctoral training under the guidance of [name] at Washington University in St. Louis indicate that approximately 27 individuals per group are needed to provide 89% power to detect differences in a similar intervention at a significance level of 0.05. This estimate uses gait velocity as the primary variable of interest and relies on a previous measured average forward gait velocity of  $1.2 \pm 0.1 \text{ m/s}$  and an average backward gait velocity of  $0.6 \pm 0.1 \text{ m/s}$  for 60 individuals with PD. The estimate is designed to detect a difference of 1 SD or  $0.1 \text{ m/s}$ , which is equivalent to an effect size of 0.4. Additionally, an attrition rate of approximately 15-20% should be expected. As the future RCT will likely focus on spatiotemporal measures collected during ADL task performance, this estimate provides some guidance for future work, but ideally future proposals will be powered from pilot data on the aims proposed herein. The proposed study of 40 individuals (20 per group) will provide pilot data which will be used to estimate effect size for the subsequent proposal (study 1).

To examine the reach of the project into the lower SES Parkinson disease community, we will analyze questions 6 and 7 of the MacArthur Scale of Subjective Social Status. A descriptive analysis of these data and subsequent comparison to income data for the state of WI will allow us to assess if individuals with PD in lower SES communities were optimally targeted.

To examine the qualitative effectiveness of the cycling intervention as well as the health coach intervention we will code the responses from the survey, assess common themes and use these data to inform the development of a larger RCT.

For both studies, we will employ a  $2 \times 2$  repeated measures ANOVA with time and intervention as the factors, to determine the outcomes of the cycling intervention effectiveness aims. Additionally, we will use a time (posttest to 3-month follow-up) by group to examine the effectiveness of the health coach maintenance model. Variables of interest include: total number of completed sessions and session duration; PASS scores, walking velocity, stride length, base of support; gait variables (velocity, stride length, base of support and % of time in double support) and MiniBESTest scores as well as number of falls; and mean daily step count.

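### Do the inherited planning figures for gait velocity (27 per group, 89% power, 1 SD, effect size 0.4) contradict each other?

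*Combined protocol and SAP*

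**What the plan says.** The paragraph opens by disclaiming a powered design: "we have not proposed a recruitment level that will properly power the outcome measures for a desired effect size". It then reports, from earlier work by a member of the study team, that "approximately 27 individuals per group are needed to provide 89% power to detect differences in a similar intervention at a significance level of 0.05". The basis is gait velocity with an SD of 0.1 m/s. "The estimate is designed to detect a difference of 1 SD or" 0.1 m/s, "which is equivalent to an effect size of 0.4". Attrition of 15–20% is mentioned as a further consideration and is not said to be included in the 27.

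The paragraph does not give the number of groups behind the estimate, the test, whether it is one- or two-sided, or whether 0.4 is Cohen's d or Cohen's f. It treats the estimate as some guidance for later work, prefers that later proposals be powered from this pilot's own data, and describes the 40 participants of Study 1 (20 per group) as a source of effect-size estimates. Under Research Design, both studies randomise to two arms. The planned effectiveness analysis is a 2 × 2 repeated measures ANOVA with time and intervention as factors.

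**The concern.** Both studies here have two arms, so a reader naturally takes the estimate as a two-arm calculation, and then the numbers do not match. With an SD of 0.1 m/s, a difference of 0.1 m/s is d = 1.0. The corresponding f for two equal groups is 0.5. Neither is 0.4, and the power at 27 per group is not 89%.

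At stake would be the planning of the follow-on trial. For 89% power in two arms, the required number per group is 22 if the target is 1 SD, 33 if 0.4 is f (d = 0.8), and 128 if 0.4 is d. Someone who took the 0.4 label at face value as d would size a trial about six times larger than someone who took the 1-SD label (128 / 22 = 5.8).

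**Working it through.** **Inputs**, all from Power and Statistical Analysis: n = 27 per group, power 89%, alpha 0.05, SD 0.1 m/s, difference 0.1 m/s, effect size 0.4. Two-sided tests are assumed because sidedness is not stated.

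**1. Reproducing the stated figures.** For a one-way ANOVA with k groups of n, the noncentrality is λ = f² × k × n, and f is the SD of the group means divided by the within-group SD.

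- Assume three groups with means at −0.5, 0 and +0.5 SD, a range of 1 SD. Then f = √[(0.25 + 0 + 0.25)/3] = √0.1667 = 0.408, which rounds to 0.4.
- With f = 0.4, k = 3 and n = 27: λ = 0.16 × 81 = 12.96 on 2 and 78 degrees of freedom, and power is 89.5%.
- With n = 26, power is 88.3%, so 27 is the smallest n that reaches 89%.
- With the unrounded f = 0.408 and n = 27, power is 90.8%.

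So 1 SD, 0.4, 27 and 89% are mutually consistent under this reading.

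**2. Simple two-arm comparison.** For a two-sample t test, the noncentrality is d × √(n/2), on 2n − 2 degrees of freedom. With n = 27, √(27/2) = 3.674.

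| Reading of the target | d | Power, 27 per group | n per group for 89% |
|---|---|---|---|
| 1 SD (f = 0.5) | 1.0 | 95.0% | 22 (90.0%; 21 gives 88.5%) |
| 0.4 is f | 0.8 | 82.2% | 33 |
| 0.4 is d | 0.4 | 30.3% | 128 |

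None of these gives 89% with 27 per group.

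**3. Two-arm comparison of change.** The time-by-intervention term of a 2 × 2 repeated measures ANOVA is a test on pre-to-post change. If 1 SD refers to velocity itself and the pre–post correlation is r, then d for change = 1/√[2(1 − r)]. The documents give no r, so a range is shown.

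| r | d for change | Power, 27 per group | Power, 20 per group |
|---|---|---|---|
| 0 | 0.71 | 72% | 59% |
| 0.3 | 0.85 | 86% | 74% |
| 0.35 | 0.88 | 88.5% | 77% |
| 0.37 | 0.89 | 89.5% | 78% |
| 0.5 | 1.00 | 95% | 87% |
| 0.7 | 1.29 | 99.6% | 98% |

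So a two-sided two-arm test can give about 89% at 27 per group, with r near 0.36, although this does not explain the 0.4.

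**4. Other readings.** A one-sided two-arm test at d = 0.8 gives 89.5% with 27 per group, but 0.8 SD contradicts the stated 1 SD. Taking 20% attrition out of 27 leaves 27 × 0.80 = 21.6; with 21 or 22 per group and d = 1.0, power is 88.5% or 90.0%. That does not explain the 0.4 either, and the text adds attrition separately. Of the readings tried, only the three-group ANOVA accounts for all four figures.

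**The case for a change.** The strongest case for a correction is that a reader who has only this document cannot recover a three-group origin. Three groups are never mentioned, while every comparison in both studies is between two arms. An estimate that matches a three-group design is offered as guidance for what is likely to be two-arm work, where it does not carry over, and a mislabelled effect-size scale is easily copied into a grant application. Rewording one paragraph would cost almost nothing.

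Part of this stands. The number of groups, the test and the effect-size scale should accompany such a figure, and in a two-arm post-test comparison 1 SD is d = 1.0, not 0.4. But the six-fold spread arises only if 0.4 is taken as d, and the neighbouring 1 SD, 27 and 89% rule that out. A planner who checks the figures sees this at once. The paragraph also directs later proposals to this pilot's data and expects a different kind of outcome, spatiotemporal measures during daily-living tasks.

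Replacing the text with a two-arm power figure for this study would make it worse. For 20 per group and a 1-SD difference, 87% (or 78–81% with the 16 or 17 left after 15–20% attrition) applies to a post-test t test. For the planned time-by-group test, power runs from 59% at r = 0 to 98% at r = 0.7. One number would claim more than the documents support, beside a correct statement that the pilot is not powered.

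**Conclusion.** The figures are under-described, not shown to be wrong. They agree with one another as a three-group one-way ANOVA with f = 0.4 (89.5% power at 27 per group). That reading is an inference from the numbers; the two-arm reading needed to call them contradictory is equally unstated, since the estimate is credited to "to detect differences in a similar intervention" in earlier work. The two-arm arithmetic behind the concern is correct for a post-test comparison (95.0% at 27 per group; 22 per group gives 90.0%), but it does not establish an error.

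No enrolment number, analysis or decision in either study uses the 0.4. Study 1 enrols 40 to estimate effect sizes, with an explicit statement that it is not powered. The gap is missing detail about an inherited figure, and anyone planning the later trial would recalculate for their own design. No change to the plan is called for.

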## Specific Aims

### **Study 1**

**SPECIFIC AIM 1:** Examine the reach and maintenance of an in-home cycling program for underserved individuals with PD. Reach will be assessed by examining the demographic characteristics of the individuals enrolled and through the administration of a questionnaire on objective and subjective socioeconomic status to better understand their level of accessibility to services, perceived barriers and economic status. We will also explore the implementation of a health coach to promote effective maintenance of the program after the 6-month intervention. Finally, we will conduct two interviews to better understand strengths and weakness of the program and to better address the needs of the participants in future studies.

**Hypothesis 1a:** Demographic characteristics including race and socioeconomic status of the enrolled participants will not statistically differ from the characteristics of the state of WI.

**Hypothesis 1b:** Feedback from participant interviews will inform future delivery of the in-home cycling program.

**SPECIFIC AIM 2:** Determine the effectiveness of a 6-month in-home, progressive, tele-exercise cycling program and 3-month health coach follow-up for underserved populations of individuals with PD.

**Hypothesis 2a:** Participants will improve performance of activities of daily living from baseline to posttest. These effects will be maintained at 3-month follow-up.

**Hypothesis 2b:** Participants will significantly improve measures of gait and balance performance and non-significantly improve fall rate from baseline to posttest. These effects will be maintained at 3-month follow-up in the group piloting implementation of a health coach, but not in solo follow-up group. Falls data will allow for effect size calculations for future applications.

**Hypothesis 2c:** Activity level as measured by an activity monitor will increase from baseline to posttest. This effect will be maintained at 3-month follow-up in health coach group, but not in the solo group.

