## Study 1 Intervention

Qualifying participants will be stratified by age and motor symptom severity as assessed by the UPDRS (UPDRS Motor score (+/- 4 points) and then randomly assigned to either the in-home cycling group or the waitlist control group.

For individuals assigned to the control group, pre-testing will occur six-months before the baseline measures are collected (figure 1). This period will allow us to collect normal care control data from each participant prior to their six months in the active phase of the study. During this period, each individual will be contacted weekly by the study team to complete a falls questionnaire. Baseline testing will occur within two weeks of the start of the Intervention. Post-test data will be collected following the 6-month intervention and will occur within 1 week of the last calendar day of the intervention.

Participants will be asked to not begin any new exercise programs once enrolled in the study, but will not be asked to discontinue any current physical activity. Information about current physical activity level will be collected at all time points.

Activity monitors (Garmin VivoSmart 3) will be donned by all study participants throughout the duration of the study starting at the time of either pre-test or baseline assessment depending on group assignment and continuing through the 3-month follow-up. These devices allow for activity monitoring as well as online monitoring of heart rate. Participants will be asked to wear the activity monitors at all times once enrolled in the study. Number of steps taken daily and amount of aerobic activity will be used to compare changes in activity level.

**Cycling** -The initial cycling session will occur in the participant's home within 2-weeks of the baseline assessment. Two members of the testing team will be present. The team will set-up the bike and properly fit it to the individual rider. Additionally, the team will ensure the stationary bike is set-up in a safe and secure manner and in an area free of clutter and dangerous obstacles. Study team member will also set-up and establish a secure connection using the MiFi device at this time. Both groups will be provided with a MiFi wireless internet connection if needed to allow for data collection of cycling and activity monitor data.

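### Must the plan define the index, contrast and confidence interval of the effect size that the pilot is to supply to the next trial?

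*Combined protocol and SAP*

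**What the plan says.** The Power and Statistical Analysis section says the pilot has no recruitment target set to power its outcomes. It cites earlier work in which about 27 per group gave 89% power at a significance level of 0.05 for a difference of 1 SD, or 0.1 m/s, in gait velocity, "which is equivalent to an effect size of 0.4". It adds that "an attrition rate of approximately 15-20% should be expected". The 40 participants of Study 1, 20 per group, "will provide pilot data which will be used to estimate effect size for the subsequent proposal", and "ideally future proposals will be powered from pilot data on the aims proposed herein". Under Specific Aims, the fall-rate hypothesis of each study carries the same promise: "Falls data will allow for effect size calculations for future applications".

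For analysis, both studies use a 2 × 2 "repeated measures ANOVA with time and intervention as the factors". A time-by-group analysis from posttest to the 3-month follow-up covers the health coach phase, and a list of variables follows. No index, standardiser or interval is named.

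The word *baseline* has two senses in Study 1. Hypothesis 2a reads "Participants will improve performance of activities of daily living from baseline to posttest". The Study 1 Intervention section says: "For individuals assigned to the control group, pre-testing will occur six-months before the baseline measures are collected". The title of the assessment list in the Baseline section, however, treats the control group's pre-test as the counterpart of the other group's baseline.

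**The concern.** A pilot that disclaims power and offers an effect size to the next trial might be expected to say what that effect size is. Three things look missing.

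- **Index and standardiser.** One difference in m/s can be written as Cohen's d, Cohen's f or partial eta squared. It can be scaled by the SD at one visit or by the SD of change.
- **Contrast.** Taken literally, baseline to posttest in the control group is its later cycling period. The phrase could then mean before-and-after cycling in everyone, which is not the randomised comparison with normal care.
- **Interval.** With 20 per group a point estimate is imprecise, and a trial sized from it alone could be far too small or far too large.

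The unlabelled 0.4 seems to show the danger. In a two-group trial at two-sided 0.05 and 89% power, 0.4 read as d needs 128 per group. Read as f, which is d = 0.8 in two groups, it needs 33 (exact t calculation).

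**Working it through.** **Inputs from the Power and Statistical Analysis section.** 27 per group, 89% power, significance level 0.05, difference 0.1 m/s, SD 0.1 m/s, effect size 0.4, 20 per group in Study 1, attrition 15–20% (20 × 0.85 = 17; 20 × 0.80 = 16). **Assumed:** pre–post correlation ρ from 0 to 0.7, because the documents give none; independent groups; an observed d of 1.0 for illustration.

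**1. The plan's own figure.** At 27 per group, two-sided 0.05:

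| Reading | Power |
|---|---|
| Two groups, d = 1.0 | 95.0% |
| Two groups, f = 0.4 (d = 0.8) | 82.2% |
| Two groups, d = 0.4 | 30.3% |
| Two groups, change score, ρ = 0.36 (f = 0.44) | 89.0% |
| Three-group ANOVA, f = 0.4 | 89.5% |

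With three groups, a 1 SD range and the third mean midway, f = √(1/6) = 0.408. So 1 SD, 0.4 and about 89% agree in a three-group layout. The documents do not state that layout, so this shows only that the figures can be consistent. The change-score row fits the power but matches 0.4 only loosely.

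**2. How far the label can move.** SD of change = 0.1 × √(2(1 − ρ)); d = 0.1 / SD of change; f = d/2; partial eta squared = f²/(1 + f²).

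| ρ | SD of change (m/s) | d | f | Partial eta squared |
|---|---|---|---|---|
| 0 | 0.141 | 0.71 | 0.35 | 0.11 |
| 0.5 | 0.100 | 1.00 | 0.50 | 0.20 |
| 0.7 | 0.077 | 1.29 | 0.65 | 0.29 |

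Each row describes the same 0.1 m/s. The columns convert into one another once the SDs and group sizes are known.

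**3. Precision.** 95% interval for an observed d of 1.0, from the noncentral t distribution, and the sample size per group at each limit (two-sided 0.05, 89% power):

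| Per group | 95% interval | Next trial, per group |
|---|---|---|
| 20 | 0.335 to 1.653 | 182 or 9 |
| 16 | 0.255 to 1.730 | 313 or 8 |

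In m/s the half-width is t(0.975, 2n − 2) × SD of change × √(2/n). At n = 20 it is 0.090 for ρ = 0 and 0.050 for ρ = 0.7. At n = 16 it is 0.102 and 0.056. These figures depend on n and the SD, not on what the plan calls the result.

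**4. Does the planned ANOVA withhold the estimate?** In a 2 × 2 layout the interaction has one degree of freedom, so t = √F and the change-score d = √F × √(2/n). With n = 20 and F = 10, d = 3.162 × 0.316 = 1.0, and its interval is the first row of step 3. Group means and SDs at the two visits, with the same F, give the difference in m/s and its interval.

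**5. Is the contrast identified?** The Research Design section randomises Study 1 participants to cycling or normal care for six months. The control group is then assessed at both ends of its normal-care period (Study 1 Intervention). The ANOVA crosses time with intervention, so its interaction compares the two arms' change over the randomised period. Pooled before-and-after cycling has no intervention factor and cannot be that 2 × 2. The title in the Baseline section, which pairs the control pre-test with the other arm's baseline, supports this reading.

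**6. Falls.** They are logged weekly in both studies, and the number of falls is a listed variable. Counts and weeks of follow-up are therefore available for a rate ratio with an interval.

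**The case for a change.** The best case for a change is that disclaiming power leaves the estimate and its uncertainty as the main quantitative product for the next trial, that a few sentences would settle the matter, and that the unlabelled 0.4 shows how such a number is misread later. Part of this stands. The section names no index, standardiser or interval. *Baseline* has two senses for the control group. A reader who meets 0.4 cannot tell d from f without reconstructing it.

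The rest does not carry a change:

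- The effect size is not the pilot's only product. It is promised for Study 1 and for falls, alongside reach, maintenance, interviews and hypothesis tests.
- The fear of false precision supposes that only a point value or a p-value will be reported. Nothing in the plan says so.
- The intervals in step 3 apply to a d scaled by the SD of the analysed score. For a difference in change scaled by the SD at one visit (0.1 m/s), step 3 gives about 1.0 ± 0.50 to 1.0 ± 0.90 at 20 per group, ignoring error in the SD. The 182-or-9 contrast illustrates small-sample imprecision and does not measure a fault in the wording.
- One reporting formula would not fit every listed variable. Completed sessions and session duration have no value before the intervention, and the health coach phase has its own contrast. Leaving the form of summary to the analyst is reasonable in a pilot.

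**Conclusion.** No change to the plan follows. The promised effect size is undefined in form, but the randomised comparison, the interaction term and the variable list determine what will be estimated. The planned data contain what is needed for differences in original units, SDs, standardised values and intervals. No stated rule is shown to give a wrong result. The 0.4 comes from earlier work, is offered as guidance for a later trial and does not set the 20 per group. It can be reconciled with 27 per group at 89% power, as 89.5% under an assumed three-group ANOVA.

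The imprecision is real: 0.335 to 1.653 around an observed d of 1.0 at 20 per group, or 0.050 to 0.090 m/s either side of the difference. It is a property of 40 participants that the section openly accepts, and naming an index would leave it as it is.

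The conclusion rests on independent groups, although participants are paired on severity and age before randomisation, so the analyst should allow for the pairing when forming intervals. It also rests on assumed correlations of 0 to 0.7 and an illustrative d of 1.0. None of these bears on whether the contrast is identified.
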